Tumor evaluation/staging during treatment (CT/MRI/other established methods) y						X (every 8 weeks)			Every 8 weeks for the first 24 weeks, then every 12 weeks thereafter	X			
Dosing													
Registration z		X											
Pretreatment aa		X	X	X	X								

		Treatment Period a (-3/+1 days) 1 Cycle = 14 Days								End Of Treatment/Follow-Up b			
Assessments	Screening (≤ 28 Days Prior to Enrollment)	Cycle 1	Cycle 2	Cycle 3	Cycle 4	Cycle 5	Cycle 6	Cycle 7	Until EOT	EOT/ Withdrawal Visit b	Safety Follow-up c		Survival Follow-up d
		Week 1 (Day 1)	Week 3 (Day 15)	Week 5 (Day 29)	Week 7 (Day 43)	Week 9 (Day 57)	Week 11 (Day 71)	Week 13 (Day 85)	> Week 13 (Day 85)	Within 7 Days of Decision to Discontinue	Visit 30 Days (± 5 days) After Last Tx	Phone Call 90 Days (± 5 days) After Last Tx	Every 12 Weeks (± 1 Week) After Last Tx
Avelumab administration bb		X	X	X	X	X	X	X	Q2 weeks				

AEs: adverse events; βhCG: beta-human chorionic gonadotropin; C1D1: Cycle 1 Day 1; CNS: central nervous system; CR: complete response; CT: computed tomography; ECG: electrocardiogram; eCRF: electronic Case Report Form; EOT: End of Treatment; CCI; HBV: hepatitis B virus; HCV: hepatitis C virus; IGF: insulin-like growth factor; MRI: magnetic resonance imaging; NCI-CTCAE: National Cancer Institute Common Terminology Criteria for Adverse Events; PD: progressive disease; PR: partial response; Q: every; QTc: corrected QT; RECIST 1.1: Response Evaluation Criteria in Solid Tumors version 1.1; SAE: serious adverse event; T4: free thyroxine; TSH: thyroid stimulating hormone; Tx: treatment.

- Treatment period: A time window of up to 3 days before and 1 day after the scheduled visit day (-3/+1 days) will be permitted for all treatment procedures. The biweekly, 14-day treatment schedule should be strictly adhered to, returning to the target date even if the previous visit was off schedule.

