#### 5.1.1.1 Phase I Study Design

In the dose-finding part of the study, subjects will be enrolled in sequential cohorts of 3 to 6 subjects each; the first 3 subjects will be  $\geq 1$  year old. At least 12 subjects must be evaluable for the primary analysis. Phase I will be completed when at least 12 DLT-evaluable subjects have been treated at a dose level confirmed to be safe. Phase II will then begin.

The starting dose will be the same as recommended dose in adults, 10 mg/kg avelumab administered intravenously (iv) once every 2 weeks, which is based on modeling and simulation results using adult PK data from ongoing avelumab studies as described in Section 5.2. Avelumab will be administered until confirmed progression, death, unacceptable toxicity, or any criterion for withdrawal occurs. In Phase I, the DLT observation period is defined as a 28-day period (2 cycles) beginning with the first avelumab administration.

The first cohort of 3 to 6 subjects will be enrolled at the starting dose level of 10 mg/kg (DL1). Based on the number of subjects experiencing DLTs at the completion of the first cohort, the dose for the next cohort of subjects can be kept the same or modified.

- If DL1 is confirmed as safe, this dose will be selected as RP2D if it provides adequate exposure in children compared with adults.
- If exposure is not adequate (when compared with adult population PK [PopPK]-simulated values for median and distribution of exposure [ $C_{max}$ , AUC, and  $C_{trough}$ ]), a decision can be made to escalate to a dose level up to 20 mg/kg (DL2).
- If at any point the modified toxicity probability interval (mTPI) results indicate a dose de-escalation is warranted, the next subjects will be enrolled at lower dose level of 3 mg/kg every 2 weeks (DL -1). Dose re-escalation can be permitted based on the mTPI results as long as the current dose level has not been determined to have exceeded the MTD. The MTD estimate is the highest dose tested of avelumab associated with the occurrence of DLTs within the first 2 cycles of treatment in < 33% of subjects, provided that a higher dose level of avelumab was tested and had an associated DLT rate  $\geq$  33%.

Subjects will return to the clinic at regular intervals for assessments (see Section 7.1 and Table 1).

Avelumab treatment will continue until:

- PD (see Section 5.5.1) or death
- Unacceptable toxicity
- Any criterion for withdrawal from the trial or trial treatment is fulfilled (see Section 5.5).

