- If DL1 is confirmed as safe, this dose will be selected as RP2D if it provides adequate exposure in children compared with adults.
- A decision can be made in a cohort defined by the SMC to test a dose level above 10 mg/kg (up to 20 mg/kg) if both of the following conditions are met:
  - Exposure achieved at 10 mg/kg does not reach therapeutic levels established in adults
  - 10 mg/kg was demonstrated to be safe.
- If a subject does not receive at least 2 infusions of avelumab within the DLT observation period (2 cycles = 28 days) for reasons other than study drug-related toxicity, another subject will be enrolled to replace that subject at the current dose level.
- Avelumab treatment will continue until:
  - Confirmed PD (see Section 5.5.1) or death
  - Unacceptable toxicity
  - Any criterion for withdrawal from the trial or trial treatment is fulfilled (see Section 5.5).
- Treatment can continue past the initial determination of confirmed disease progression per irRECIST (see Section 6.2).
- Phase I will be completed when at least 12 DLT-evaluable subjects have been treated at a dose level confirmed to be safe and similar exposure to that in adults is achieved.
- Additional subjects (up to 6 per cohort) can be enrolled at any dose level determined to be below the MTD to further assess variability of PK or safety by age.

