## 8.4 Analysis Sets

**Full Analysis Set (FAS):** All subjects enrolled in the study and receive at least 1 dose of avelumab.

**Safety Analysis Set (SAF):** All subjects who receive at least 1 dose of avelumab. In this trial, the SAF = FAS.

**Per-Protocol (PP) Analysis Set:** A subset of the FAS; will include all FAS subjects who did not have any clinically important protocol deviations.

**DLT Analysis Set (Phase I only):** All subjects with data used for implementing the dose escalation schedule. These subjects will have received all trial treatment administrations in the DLT evaluation period (first 2 cycles of treatment) or stopped treatment because of DLTs in the DLT evaluation period.

**PK Analysis Set:** All subjects who complete at least 1 administration of avelumab and who provide at least 1 sample with measurable concentrations of avelumab (at least 1 predose and 2 postdose from 2 or more treatment cycles).

**Immunogenicity Analysis Set:** All subjects who complete at least 1 administration of avelumab, and who have provided a blood sample prior to any avelumab treatment and at least 1 post-treatment sample.

**Biomarker Analysis Sets:** All subjects who complete at least 1 administration of avelumab, and who have provided the appropriate blood/serum/plasma samples for biomarker assessments.

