8.2 Definition of Analysis Sets and Subgroups

Screening Analysis Set (SCR)

The screening analysis set includes all subjects who signed the informed consent.

Full Analysis Set (FAS)

The full analysis set (FAS) will include all enrolled subjects who receive any dose of avelumab.

Safety Analysis Set (SAF)

The safety analysis set (SAF) will include all enrolled subjects who were administered any dose of avelumab. Analyses performed on the safety set will consider subjects as treated. In this non-randomized study, the FAS and the SAF will be identical.

Dose Limiting Toxicity (DLT) Analysis Set

The DLT analysis set includes all subjects who meet either of the following criteria:

- Have received 100% of all planned doses of treatment during the DLT evaluation period (first 2 cycles of treatment) and have been followed for at least 28 days
- Have stopped treatment because of a DLT in the DLT evaluation period

Pharmacokinetic (PK) Analysis Set

The PK Analysis Set will consist of all subjects who receive at least one dose of avelumab, have no important protocol deviations or important events affecting PK, and provide at least one measurable post-dose concentration. Subjects will be analyzed according to the actual treatment they received. All PK analyses will be based on this analysis set.

Immunogenicity Analysis Set

The immunogenicity analysis set will include all subjects who receive any dose of avelumab and who have at least one valid ADA result (including negative, positive-TNR).

Biomarker Analysis Set

Biomarker analysis set will include all subjects who receive any dose of avelumab and who have provided at least one blood, serum, plasma, or tumor sample for biomarker assessments.

Table 1 summarizes the use of the analysis sets in the different analyses.

Table 1 Statistical Analysis by Analysis Set

Analyses	Screening Analysis Set	Full Analysis Set	Safety Analysis Set	DLT Analysis Set	PK Analysis Set	Immunogenicity Analysis Set	Biomarker Analysis Set
Baseline Characteristics	✓	✓	✓				
Prior and Concomitant Therapies		✓	✓				
Compliance and Exposure			✓				
Primary Endpoint			✓	✓			
Secondary Endpoint		✓			✓	✓	✓
CCI							
Safety			✓				

9 General Specifications for Data Analyses

[figure not shown]
Throughout this document “start date” is the date of first dose of study treatment.

Data handling after cut-off date:

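### Replacement rule, protocol DLT set and SAP DLT set test evaluability differently: a DLT-free child lost after infusion 2 but before 28 days is not replaced, yet drops out of the SAP set

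*Protocol*

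**What the plan says.** Four places bear on whether a subject counts for DLT.

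- **Replacement, Protocol 5.1.1.1.1 (rules after Table 3).** "If a subject does not receive at least 2 infusions of avelumab within the DLT observation period" and the cause is not drug toxicity, a substitute is enrolled: "for reasons other than study drug-related toxicity, another subject will be enrolled to replace that subject at the current dose level". The rule has no test for completeness of dose or length of observation.
- **Protocol DLT Analysis Set, 8.4.** "These subjects will have received all trial treatment administrations in the DLT evaluation period", or they stopped because of a DLT. No duration of follow-up is given.
- **SAP DLT Analysis Set, 8.2.** "Have received 100% of all planned doses of treatment during the DLT evaluation period" (the first two cycles) "and have been followed for at least 28 days", or alternatively "Have stopped treatment because of a DLT in the DLT evaluation period".
- **Table 3 and its text, Protocol 5.1.1.1.1, repeated in SAP 15.1.** The decision table is entered by the number of subjects treated at the current dose, and the text says that all subjects treated at that dose are used.

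Protocol 5.1.1.1 adds: "At least 12 subjects must be evaluable for the primary analysis". SAP Section 7 says that its methods accord with protocol version 2.0. It explains changes to the PK, immunogenicity and biomarker sets and mentions none to the DLT set.

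**The concern.** The DLT rate is a Phase I primary endpoint, and the DLT Analysis Set is the stated basis for the MTD (Protocol 8.5.1). The set should have one definition, and the replacement rule should restore exactly the subjects that the definition removes. Here it does not. Infusion 2 comes about halfway through the 28-day window. Once it is given, the replacement rule is satisfied whatever happens next, while the SAP set still requires the rest of the window to be observed.

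At stake is the denominator on which a cohort decision is taken. If a child who was only partly observed is counted as DLT-free among those treated, the observed rate is lower than on the fully observed subjects. If the child is not counted, a small cohort may shrink to a size for which Table 3 has no entry, and nothing in the replacement rule refills it.

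**Working it through.** **1. When the gap opens.** Infusion 2 is due on Day 15 (Table 1). The Table 1 footnote on the treatment period allows "A time window of up to 3 days before and 1 day after the scheduled visit day", so it falls on Days 15 − 3 = 12 to 15 + 1 = 16. If the day of first dose is Day 1, a child observed through Day 28 arguably has 28 days. The gap therefore runs from infusion 2 to about Day 27. A child lost straight after a Day 15 infusion has 28 − 15 = 13 of the 28 days unobserved.

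**2. Cases side by side.**

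| Case | Replaced? | Protocol 8.4 set | SAP 8.2 set |
|---|---|---|---|
| Two full infusions, no DLT, follow-up ends before 28 days | No | In | Out |
| Two infusions, one cut short for a non-toxicity reason, followed 28 days | No | In, if administrations are counted | Out only if 100% refers to amount |
| Fewer than two infusions, non-toxicity reason | Yes | Out | Out |
| Fewer than two infusions because of drug toxicity (itself a DLT, Protocol 5.1.1.1.2) | No | In | In |
| Stops drug after infusion 2, still followed to 28 days | No | In | In |

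The first row is the definite conflict. The second depends on a wording that the SAP leaves open. The other three agree.

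**3. Reproducing Table 3.** Inputs from Protocol 5.1.1.1.1: target 0.30, e1 = 0.05, e2 = 0.03. Assumed, because the documents do not state them: a Beta(1,1) prior, and DU when P(p > 0.30) > 0.95. With x DLTs in n subjects the posterior is Beta(1 + x, 1 + n − x). For each of the intervals (0, 0.25), (0.25, 0.33) and (0.33, 1), unit probability mass = posterior probability ÷ interval length, and the interval with the largest value gives the decision. This matches all 88 decision cells (90 cells less two NA).

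**4. Effect of one such child.** Keep the DLT count and read Table 3 at n treated and at n − 1 evaluable. For n = 3 to 12 and x = 0 to n − 1 there are 3 + 4 + … + 12 = 75 comparisons, of which 12 change:

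- Stay becomes de-escalate, four cells: 2/4 against 2/3, 3/7 against 3/6, 4/9 against 4/8, 5/11 against 5/10.
- No rule, one cell: 0/3 is E, while 0/2 is NA.
- D becomes DU, five cells: 2/3, 3/5, 4/7, 5/10 and 6/12 treated. Both de-escalate now, but DU also labels the dose unacceptably toxic.
- E becomes S, two cells: 1/6 and 2/12 treated. At DL1, E ordinarily means staying at DL1, so these rarely matter there.

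The observed rate is lower each time on the treated denominator, for example 3/7 = 42.9% against 3/6 = 50.0%.

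**5. How often.** The documents give no rate for loss between infusion 2 and Day 28. With assumed rate q, the chance of at least one such child among m is 1 − (1 − q)^m:

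| q (assumed) | m = 3 | m = 6 | m = 12 | Enrol for 12 evaluable, 12/(1 − q) rounded up |
|---|---|---|---|---|
| 5% | 14% | 27% | 46% | 13 |
| 10% | 27% | 47% | 72% | 14 |
| 20% | 49% | 74% | 93% | 15 |

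**The case against.** Much of the possible harm is contained by other text.

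- **A reader might infer that Phase I can close with fewer than 12 in the analysis set.** The documents do not support that as a consequence. Protocol 5.1.1.1, 5.1.1.1.1 and 5.1.1.1.6 tie completion to 12 evaluable subjects, and enrolment may run to 36. Replacement and counting are separate rules. The protection does depend on counting with the SAP set, because the protocol's own set is looser.
- **A reader might infer that the SMC and the final report use different sets.** SAP Section 6 gives the SMC DLT results on the DLT Analysis Set, and SAP 15.1 reports on the same set. What remains is narrower: the decision table beside those results is headed by subjects treated.
- **A reader might infer that any child who leaves treatment is affected.** Stopping drug does not end observation. There is a visit 30 days after the last dose (Protocol 7.1.4), and withdrawn subjects are asked to continue safety follow-up (5.5.2).
- **A reader might move the MTD estimate from 3/12 = 25.0% to 3/9 = 33.3%.** That needs three such children among 12, with probability about 2% at q = 5% and 11% at q = 10%, and nine evaluable would not complete Phase I.
- **The protocol may already intend 28 days.** Protocol 5.1.1.1.1 opens later cohorts once the evaluable subjects have been evaluated for two cycles, or earlier if more than one has a DLT. This supports the SAP's reading, but it neither amends 8.4 nor triggers replacement.
- **The events may be rare.** Eligibility requires a life expectancy of at least 3 months and excludes rapidly progressive disease. The four stay-to-de-escalate cells need observed DLT rates of 43% to 50% on the treated denominator, and no MTD was reached in adults up to 20 mg/kg.

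These points limit the size. They do not remove the conflict among the replacement rule, the two set definitions and the table heading.

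**Conclusion.** The concern holds as an undeclared inconsistency in the set for a primary endpoint. One kind of subject falls between the rules: no DLT, infusion 2 received, observation ended before 28 days by death, loss or refusal. A shortened infusion joins it only if the SAP's 100% means amount rather than number of doses.

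The consequence is local to cohort decisions. One such child changes 12 of 75 Table 3 readings. Four of these go from stay to de-escalate, and one has no rule. The 12-subject minimum is not lost if it is counted on the SAP set. The cell counts come directly from Table 3. The frequencies rest on assumed leaving rates of 5% to 20% and should be read as a range. The alignment is worth making because it is specific and cheap, not because the recommended dose has been shown to be at risk.

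**What to change.** Reconcile Protocol 5.1.1.1.1, Protocol 8.4, SAP 8.2 and the Table 3 denominator (also Table 5 in SAP 15.1) to one definition, the SAP's full-window set:

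1. Replace any subject without a DLT who is not observed to the end of the 28-day window or does not receive the planned infusions for a non-toxicity reason.
2. Enter only that set in Table 3, and relabel its columns as evaluable subjects.
3. Count only that set toward the 12.
4. State whether 100% of planned doses means amount or number of doses.

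The cost is wording and an occasional replacement subject, within the planned 12 to 36.

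The SAP's modification history says that monotherapy evaluation ended after Phase I, so a new replacement rule may come too late to change enrolment. If enrolment has closed, declare the DLT-set difference in SAP Section 7, report the DLT rate with its Clopper-Pearson interval under both definitions, and list any child who is in one set but not the other.

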### 5.1.1.1.2 Definition of Dose-limiting Toxicity

Severity of AEs will be graded according to NCI-CTCAE version 4.03. For the purpose of dose finding, any of the following AEs occurring during the primary DLT observation period (28-day period [2 treatment cycles]) that are attributable to avelumab will be classified as DLTs:

#### Hematologic:

1. Grade 4 neutropenia of > 7 days in duration
2. Grade  $\geq$  3 neutropenic infection
3. Grade  $\geq$  3 thrombocytopenia with bleeding
4. Grade 4 thrombocytopenia > 7 days
5. Grade 4 anemia.

#### Nonhematologic:

1. Any Grade  $\geq$  3 toxicity, except for any of the following:
  - a. Transient ( $\leq$  72 hours) Grade 3 flu-like symptoms or fever, which is controlled with medical management
  - b. Transient ( $\leq$  72 hours) Grade 3 fatigue, local reactions, headache, nausea, or emesis that resolves to Grade  $\leq$  1 or to baseline
  - c. Grade 3 diarrhea or Grade 3 skin toxicity that resolves to Grade  $\leq$  1 in less than 7 days after medical management (eg, immunosuppressant treatment) has been initiated
  - d. Grade  $\geq$  3 amylase or lipase abnormality that is not associated with clinical manifestations of pancreatitis
  - e. Tumor flare phenomenon, defined as local pain, irritation, or rash localized at sites of known or suspected tumor
  - f. Single laboratory values out of normal range that are unlikely related to trial treatment according to the Investigator, do not have any clinical correlate, and resolve to Grade  $\leq$  1 or Baseline within 7 days with adequate medical management.
2. Inability to complete at least 2 infusions of avelumab during the DLT observation period due to treatment-related toxicity.

While the rules for adjudicating DLTs in the context of dose finding/dose expansion phases are specified above, an AE not listed above, or an AE meeting the DLT criteria above but occurring outside of the DLT observation period, may be defined as a DLT after consultation between Sponsor and Investigator, based on the emerging safety profile.

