**Table 5 Management of Immune-related Adverse Events**

Gastrointestinal irAEs		
Severity of Diarrhea/Colitis (NCI-CTCAE v4.03)	Management	Follow-up
Grade 1 Diarrhea: < 4 stools/day over Baseline Colitis: asymptomatic	Continue avelumab therapy Symptomatic treatment, eg, loperamide)	Close monitoring for worsening symptoms Educate subject to report worsening immediately If worsens: Treat as Grade 2, 3, or 4
Grade 2 Diarrhea: 4 to 6 stools per day over Baseline; iv fluids indicated < 24 hours; not interfering with ADL Colitis: abdominal pain; blood in stool	Delay avelumab therapy Symptomatic treatment	If improves to Grade 1: Resume avelumab therapy  If persists > 5 to 7 days or recurs: Treat as Grade 3 to 4
Grade 3 to 4 Diarrhea (Grade 3): ≥ 7 stools per day over Baseline; incontinence; iv fluids ≥ 24 hours; interfering with ADL Colitis (Grade 3): severe abdominal pain, medical intervention indicated, peritoneal signs Grade 4: life-threatening, perforation	Withhold avelumab for Grade 3 Permanently discontinue avelumab for Grade 4 or recurrent Grade 3. 1.0 to 2.0 mg/kg/day prednisone or equivalent Add prophylactic antibiotics for opportunistic infections Consider lower endoscopy	If improves: Continue steroids until Grade 1, then taper over at least 1 month, resume avelumab therapy following steroids taper (for initial Grade 3).  If worsens, persists > 3 to 5 days, or recurs after improvement: Add infliximab 5 mg/kg (if no contraindication), Note: Infliximab should not be used in cases of perforation or sepsis
Dermatological irAEs		
Grade of Rash (NCI-CTCAE v4.03)	Management	Follow-up
Grade 1 to 2 Covering ≤ 30% body surface area	Continue avelumab therapy Symptomatic therapy (eg, antihistamines, topical steroids)	If persists > 1 to 2 weeks or recurs: Withhold avelumab therapy Consider skin biopsy Delay avelumab therapy Consider 0.5 to 1.0 mg/kg/day prednisone or equivalent. Once improving, taper steroids over at least 1 month, consider prophylactic antibiotics for opportunistic infections, and resume avelumab therapy following steroids taper If worsens: Treat as Grade 3 to 4

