Grade 3 to 4 Covering > 30% body surface area; life threatening consequences	Withhold avelumab for Grade 3. Permanently discontinue for Grade 4 or recurrent Grade 3 Consider skin biopsy Dermatology consult	If improves to Grade 1: Taper steroids over at least 1 month and add prophylactic antibiotics for opportunistic infections Resume avelumab therapy following steroids taper (for initial Grade 3).

	1.0 to 2.0 mg/kg/day prednisone or equivalent	
Pulmonary irAEs		
Grade of Pneumonitis (NCI-CTCAE v4.03)	Management	Follow-up
Grade 1 Radiographic changes only	Consider withholding avelumab therapy Monitor for symptoms every 2 to 3 days Consider pulmonary and infectious disease consults	Re-assess at least every 3 weeks If worsens: Treat as Grade 2 or Grade 3 to 4
Grade 2 Mild to moderate new symptoms	Withhold avelumab therapy Pulmonary and Infectious Disease consults Monitor symptoms daily, consider hospitalization 1.0 to 2.0 mg/kg/day prednisone or equivalent Consider bronchoscopy, lung biopsy	Re-assess every 1 to 3 days If improves: When symptoms return to near Baseline, taper steroids over at least 1 month, consider prophylactic antibiotics for opportunistic infections, and then resume avelumab therapy following steroids taper If not improving after 2 weeks or worsening: Treat as Grade 3 to 4
Grade 3 to 4 Grade 3: Severe new symptoms; New/worsening hypoxia; Grade 4: life threatening	Permanently discontinue avelumab therapy Hospitalize Pulmonary and Infectious Disease consults 1.0 to 2.0 mg/kg/day prednisone equivalent Add prophylactic antibiotics for opportunistic infections Consider bronchoscopy, lung biopsy	If improves to Baseline: Taper steroids over at least 6 weeks If not improving after 48 hours or worsening: Add additional immunosuppression (eg, infliximab, cyclophosphamide, iv immunoglobulin, or mycophenolate mofetil)
Hepatic irAEs		
Grade of Liver Test Elevation (NCI-CTCAE v4.03)	Management	Follow-up
Grade 1 Grade 1 AST or ALT > ULN to 3.0 x ULN and / or total bilirubin > ULN to 1.5 x ULN	Continue avelumab therapy	Continue liver function monitoring If worsens: Treat as Grade 2 or 3 to 4

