15.1 Dose-Limiting Toxicities (Primary Endpoint - Phase I)

Analysis Set: DLT

The primary endpoint of the Phase 1 study is the incidence of DLTs occurring during the DLT evaluation period (28-day period, first 2 cycles of treatment) in order to determine the RP2D. DLTs are collected on the “Adverse Events Details” form on the eCRF and are recorded as the answer (“Yes” or “No”) to “Is this adverse event a dose limiting toxicity?” A DLT is defined as a toxicity of interest judged to be related to avelumab by the investigator and/or the SMC using the National Cancer Institute – Common Terminology Criteria for Adverse Events (NCI-CTCAE) version 4.03. Per the NCI-CTCAE, a DLT is defined as any of the following toxicities at any dose level and judged to be related to the study drug by the investigator and/or the SMC:

- Grade 4 neutropenia for more than 7 days
- Grade ≥ 3 febrile neutropenic infection
- Grade ≥ 3 thrombocytopenia with bleeding
- Grade 4 thrombocytopenia for more than 7 days
- Grade 4 anemia
- Any Grade ≥ 3 toxicity, except for the following:
 - Transient (≤ 72 hours) grade 3 flu-like symptoms or fever, which is controlled with medical management
 - Transient (≤ 72 hours) grade 3 fatigue, local reactions, headache, nausea, or emesis that resolves to grade ≤ 1 or to baseline
 - Grade 3 diarrhea or Grade 3 skin toxicity that resolves to Grade ≤ 1 in less than 7 days after medical management (eg immunosuppressant treatment) has been initiated

- Grade ≥ 3 amylase or lipase abnormality that is not associated with clinical manifestations of pancreatitis
- Tumor flare phenomenon, defined as local pain, irritation, or rash localized at sites of known or suspected tumor
- Single laboratory values out of normal range that are unlikely related to study drug according to the Investigator, do not have any clinical correlate, and resolve to Grade ≤ 1 or Baseline within 7 days with adequate medical management
- Inability to complete at least 2 infusions of avelumab during the DLT observation period due to treatment-related toxicity

While the rules for adjudicating DLTs are specified above, an AE not listed above, or an AE meeting the DLT criteria above but occurring outside of the DLT observation period, may be defined as a DLT after consultation between Sponsor and Investigator, based on the emerging safety profile. DLTs may be identified by the site investigator or by the SMC. Analyses of DLTs will be conducted as per the SMC assessment.

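### For immune-related Grade 3 diarrhea or skin toxicity before the second infusion, DLT exemption 1c has no effect, and the child can fall outside the DLT Analysis Set even when counted as a DLT

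*Protocol*

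**What the plan says.** - **DLT definition (protocol 5.1.1.1.2, repeated in SAP 15.1).** The lead-in covers "any of the following AEs occurring during the primary DLT observation period" that are attributable to avelumab. Nonhematologic item 1 is any Grade 3 or higher toxicity, with exceptions a to f. Exception c removes Grade 3 diarrhea or skin toxicity that falls to Grade 1 or lower "in less than 7 days after medical management (eg, immunosuppressant treatment) has been initiated". Item 2 stands apart from these exceptions: "Inability to complete at least 2 infusions of avelumab during the DLT observation period due to treatment-related toxicity".
- **Management (protocol Table 5).** For a first Grade 3 diarrhea or colitis, avelumab is withheld. Steroids continue to Grade 1, "then taper over at least 1 month, resume avelumab therapy following steroids taper (for initial Grade 3"). For a first Grade 3 rash, avelumab is withheld, steroids are tapered over at least 1 month, and then: "Resume avelumab therapy following steroids taper (for initial Grade 3").
- **Discontinuation (protocol 5.1.3.2).** The same short-lived Grade 3 diarrhea or skin toxicity is exempt from permanent discontinuation.
- **Replacement (protocol 5.1.1.1.1).** If a child has fewer than 2 infusions in the window "for reasons other than study drug-related toxicity, another subject will be enrolled to replace that subject at the current dose level".
- **DLT Analysis Set (SAP 8.2; protocol 8.4 is similar).** A subject enters by receiving every planned dose in the first 2 cycles or by meeting the alternative: "Have stopped treatment because of a DLT in the DLT evaluation period".
- **Recording and analysis (SAP 15.1).** Each AE record asks "Is this adverse event a dose limiting toxicity", answered Yes or No. The analysis follows the SMC assessment.

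**The concern.** One rule exempts an event from being a DLT. Another, followed as written, stops the child from completing 2 infusions in the window, and that failure is itself a DLT. The exemption is cancelled for one class of events without any passage saying so. Because 5.1.3.2 treats the same event as tolerable, a site or committee member could reasonably take 1c at face value.

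The analysis set adds a second problem. It recognises children who were fully dosed and children who stopped. This child was withheld and may resume, which is neither. DLTs are a primary endpoint of Phase I, they feed the mTPI decision, and the DLT Analysis Set is the stated basis for determining the MTD. With cohorts of 3 to 6, one child matters.

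**Working it through.** **1. The plan's own decision table.** Inputs from protocol 5.1.1.1.1: target 0.3, e1 = 0.05, e2 = 0.03, so the intervals are (0, 0.25), (0.25, 0.33) and (0.33, 1). For x DLTs in n subjects, the unit probability mass of an interval is its posterior probability under Beta(1 + x, 1 + n − x) divided by its length. The largest mass gives E, S or D. D becomes DU when P(p > 0.3) > 0.95. The Beta(1,1) prior and the 0.95 cut-off are assumptions, because the documents give neither. All 73 cells checked (0 to 7 DLTs) match Table 3. Cut-offs of 0.90, 0.85 and 0.80 give 7, 9 and 13 mismatches. Table 3 is therefore read as printed.

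**2. Timing.** The window is Day 1 to Day 28. The second infusion is due on Day 15 with a −3/+1 day window, so Day 12 to Day 16.

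Earliest restart day = onset day + days to Grade 1 + taper. An exempt event takes 0 to 6 whole days to resolve if management starts at onset. One month is taken as 28 or 30 days; 28 is the most favourable choice.

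| Onset | 0 + 28 | 0 + 30 | 6 + 28 | 6 + 30 |
|---|---|---|---|---|
| Day 1 | 29 | 31 | 35 | 37 |
| Day 7 | 35 | 37 | 41 | 43 |
| Day 14 | 42 | 44 | 48 | 50 |

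Every entry is later than Day 28. An event managed under Table 5 with onset before the second infusion therefore always costs that infusion within the window, and item 2 is met. If onset follows the second infusion, 2 infusions are already complete, item 2 is not met and 1c works as written.

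**3. Place in the analysis set.**
- All planned doses received: no, because the second was withheld.
- Stopped because of a DLT: not on a strict reading, because Table 5 withholds and resumes, and 5.1.3.2 does not require permanent discontinuation. If the event is coded No, this criterion fails outright.
- Replaced: no, because the cause is drug-related.

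**4. Effect on the count.** One such child, with the other children's DLTs held fixed:

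| Other DLTs | Child excluded | Child counted as a DLT |
|---|---|---|
| 1 | 1/2: S | 2/3: D |
| 2 | 2/5: S | 3/6: D |
| 3 | 3/11 = 27.3%: S | 4/12 = 33.3%: S |

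If the child is coded No but kept in the denominator, the left-hand entries become 1/3 (S), 2/6 (S) and 3/12 = 25.0% (S). The contrast with the right-hand column is unchanged. With no other DLT among 3 children at DL1, counting the event gives 1/3 (S), and DL1 is kept.

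**The case against.** The strongest reply is that nothing contradicts itself. The lead-in makes any one listed item sufficient, and exceptions a to f belong to item 1 only. Item 1 can be seen as grading severity and item 2 as capturing failure to deliver treatment. Read literally, the answer is Yes. This stands. A reader might infer that the same event is both No and Yes in the primary endpoint; the text does not support that. What remains is that 1c is emptied for these events without a stated precedence.

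Second, one body decides. The SMC rules on DLTs (protocol 2.3) and the analysis follows it (SAP 15.1), so site and committee answers do not compete. That also stands, and the SMC Charter is not among the documents. But the plan gives the committee no rule for this case. The discretion clause covers AEs that are not listed or fall outside the window, not two listed items that collide.

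Third, scope. Table 5 governs immune-related events, whereas 1c mentions immunosuppressants only as an example. A reader might infer that every Grade 3 diarrhea or skin event is affected; it is not. Protocol 5.2 does tell investigators to manage suspected immune-mediated events without another confirmed cause as immune-related, so the overlap may be large.

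Fourth, Phase I still needs at least 12 DLT-evaluable subjects, so an unreplaced child does not lower that minimum. True, but it does not settle how this child is counted.

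Fifth, protocol 5.5.1 lists Grade 3 or higher reactions among grounds for withdrawal, which might make the child one who stopped. It refers to 5.1.3.2, however, where this event is exempt.

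**Conclusion.** The point holds for Grade 3 diarrhea or skin toxicity that meets 1c, is managed under Table 5, and begins before the second infusion, which is about the first half of the 28-day window. For these events 1c has no effect, and a strict reading of the analysis set can remove a counted DLT from the DLT rate.

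One such child can change stay to de-escalate at n = 3 or n = 6, but only if other children have DLTs (1 and 2 respectively in the cases shown). At n = 12 a reader might infer a changed dose decision; Table 3 says stay at both 3/11 and 4/12. The rate does cross the 33% limit used in the MTD definition, but that alone does not fix an MTD, which also depends on the rate at another tested dose.

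The result rests on a taper of at least 28 days and on taking the word stopped strictly. The documents give no expected frequency for such events, so how often this would occur is unknown. No view is taken on which clinical rule is right.

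**What to change.** - Reconcile items 1c and 2 of protocol 5.1.1.1.2, section 5.1.3.2, Table 5, the replacement rule in 5.1.1.1.1, and SAP 15.1.
- State in 5.1.1.1.2 and SAP 15.1 whether a dose withheld only because of an event exempt under item 1 counts under item 2. Make replacement follow that answer.
- Reword the DLT Analysis Set in protocol 8.4 and SAP 8.2 so that every subject with an SMC-confirmed DLT in the window is included, whether treatment was stopped or withheld.
- In SAP 15.1, show the DLT rate with and without events that are DLTs through item 2 only and whose cause is exempt under item 1.

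The cost is a few sentences, one table row, and assigning each DLT to its item. SAP version 2.0 records that monotherapy evaluation ended after Phase I, so the protocol wording may no longer affect dosing. The analysis-set wording and the extra row still bear on the final Phase I report, which that SAP governs.
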